DMC:	Data Monitoring Committee
e-CRF:	electronic case report form
ECG:	electrocardiogram
ECHO:	echocardiography
ERT:	enzyme replacement therapy
ETP:	extension treatment period
FEV1:	forced expiratory volume in the first second of the FVC maneuver
FVC:	forced vital capacity
GAA:	lysosomal acid α -glucosidase
GLI:	global lung initiative
GMFCS-E&R:	Gross Motor Function Classification System - Expanded and Revised
GMFM-88:	Gross Motor Function Measure-88
HLGT:	high-level group term
HLT:	high-level term
HRQOL:	health-related quality of life
IAR:	infusion associated reaction
IMP:	investigational medicinal product
IOPD:	infantile-onset Pompe disease
IPFD:	interpalpebral fissure distance
IRT:	interactive response technology
IV:	intravenous

LLT:	lower-level term
Leiter-3:	Leiter International Performance Scale, Third Edition
LVM:	left ventricular mass
LVMI:	left ventricular mass index
MedDRA:	medical dictionary for regulatory activity
MEP:	maximum expiratory pressure
MIP:	maximum inspiratory pressure
mITT:	modified intent-to-treat
MPD:	margin pupil distance
MRD:	minimal required dilution
MRD-1:	margin reflex distance-1
MTD:	maximum tolerated dose
n:	number
NAb:	neutralizing antibody
NYHA:	the New York Heart Association
PAP:	primary analysis period
PCSA:	potentially clinically significant abnormality
PD:	pharmacodynamics
PDIS:	Pompe disease impact scale
PDSS:	Pompe disease symptom scale
PE:	physical examination
PEDI:	Pediatric Evaluation of Disability Inventory
PFT:	Pulmonary Function Test
PK:	pharmacokinetics
PP:	per protocol
PR:	interval from the beginning of the P wave until the beginning of the QRS complex
PT:	preferred term
PY:	patient year
QMFT:	Quick Motor Function Test
qow:	every other week
QRS:	interval from start of the Q wave to the end of the S wave
QT:	interval between the start of the Q wave to the end of the T wave
QTc:	QT interval corrected for heart rate
RR:	interval between the peaks of successive QRS complex
SAE:	serious adverse event
SD:	standard deviation
SMQ:	standard MedDRA query
SOC:	system organ class
TEAE:	treatment-emergent adverse event
ULN:	upper limit of normal
VAS:	Visual Analogue Scale
Vd:	volume of distribution
WHO-DD:	World Health Organization-Drug Dictionary
Z-score:	standard score

1 OVERVIEW AND INVESTIGATIONAL PLAN

1.1 STUDY DESIGN AND RANDOMIZATION

ACT14132 is a multi-stage phase 2 open-label, multicenter, multinational, ascending dose cohort, repeated intravenous infusion study of avalglucosidase alfa in pediatric patients with infantile-onset Pompe disease (IOPD) who have been previously treated with alglucosidase alfa and demonstrated clinical decline (Stage 1) or sub-optimal clinical response (Stage 2) in specified respiratory function, motor skills, cardiac parameters, and/or presence of ptosis.

Stage 1:

- Cohort 1 – at least 5 IOPD patients will receive avalglucosidase alfa at 20 mg/kg every other week (qow) for 6 months.
- Cohort 2 – at least 5 IOPD patients will receive avalglucosidase alfa at 40 mg/kg qow for 6 months.

Stage 2:

- Cohort 3 – at least 10 IOPD patients will be randomized 1:1 to receive avalglucosidase alfa at the highest tolerated avalglucosidase alfa dose in Stage 1 (20 mg/kg qow or 40 mg/kg qow) or alglucosidase alfa treatment at current stable dose (defined by dose of alglucosidase alfa administered regularly for a minimum of 6 months immediately prior to study entry) for 6 months.

If determined safe by an independent Data Monitoring Committee (DMC) after the 3rd patient in the 20 mg/kg qow group (Cohort 1) has received the 3rd infusion of avalglucosidase alfa, and after 5 patients have started treatment in Cohort 1, the next cohort of avalglucosidase alfa at higher dose (40 mg/kg qow) will be initiated (Cohort 2). Cohort 3 will be initiated after determination of the highest tolerated avalglucosidase alfa dose in Cohort 1 and Cohort 2 after at least 5 patients in Cohort 1 and at least 5 patients in Cohort 2 have received the 7th dose of avalglucosidase alfa (or completed Week 13 with a minimum of 6 infusions).

Upon confirmation by the Investigator or sub-Investigator (if appropriately delegated) that the patient meets all eligibility criteria and completion of the screening and baseline assessments, in Stage 2 of the study (Cohort 3), at least 10 eligible IOPD patients will be randomized 1:1 to receive avalglucosidase alfa at the highest tolerated avalglucosidase alfa dose in Stage 1 or alglucosidase alfa treatment at current stable dose for 6 months (defined by dose of alglucosidase alfa administered regularly for a minimum of 6 months immediately prior to study entry). The randomization will be stratified on gender.

After completion of treatment for 6 months (Week 25) and data collection for the primary analysis, the patients will continue on long-term avalglucosidase alfa treatment and follow-up in the Extension Period for up to a total of 3 years in the study. Cohort 3 patients receiving alglucosidase alfa will have the option to switch to treatment with avalglucosidase alfa maximum tolerated dose (MTD) as determined based on safety data from both dose levels in Cohort 1 and Cohort 2 in the extension period or discontinue the study. The data cut-off for the primary

analysis will be after the last patient in Cohort 3 has completed 6 months of treatment (Week 25) and analysis will be conducted on all data available by then.

Safety, efficacy, PK and [REDACTED] will be performed at scheduled visits throughout the study treatment period. Ventilator use, adverse events (AEs) and concomitant and pre-infusion medications/therapies will be monitored continuously throughout the study.

If a patient in Cohort 1, receiving 20 mg/kg qow avalglucosidase alfa, experiences further clinical decline at or after Week 25 when compared to prior to enrollment in ACT14132, and as defined by more rapid worsening of criteria of clinical decline, which is sustained on repeated study assessments, the patient may be managed per the discretion of the Investigator, which may include return to treatment with commercially available alglucosidase alfa (and termination of study participation) or increasing the avalglucosidase alfa dose to 40 mg/kg qow or MTD, once established, while being enrolled in the extension period of the study.

If a patient in Cohort 2 or 3 experiences further clinical decline at or after Week 25 as defined by more rapid worsening of criteria of clinical decline than prior to study start, which is sustained on repeated study assessments, the patient may be managed per the discretion of the Investigator. This may include return to treatment with commercially available alglucosidase alfa (and termination of study participation).

Patients must have completed the 25-week treatment period of the study before dose increase of avalglucosidase alfa (or start of avalglucosidase alfa for patients receiving alglucosidase alfa in Cohort 3) will be considered.

1.2 OBJECTIVES

1.2.1 Primary objectives

The primary objective of the study is to evaluate the safety profile of avalglucosidase alfa in patients with IOPD previously treated with alglucosidase alfa.

1.2.2 Secondary objectives

Secondary objectives are to characterize the pharmacokinetic (PK) profile of avalglucosidase alfa and to evaluate the preliminary efficacy of avalglucosidase alfa in comparison to alglucosidase alfa.

1.2.3 Other objectives

Additional objectives are to determine [REDACTED] effect of avalglucosidase alfa treatment on functional endurance, respiratory function, health-related quality of life (HRQOL), pain, developmental disability, and hearing in patients with IOPD.

1.3 DETERMINATION OF SAMPLE SIZE

[figure not shown]
No formal sample size calculations have been performed. Sample size for this study was based upon empirical considerations.

1.4 STUDY PLAN

For each patient who signs the informed consent, the study consists of:

- An up to 14-day screening period (may be extended to up to 4 weeks in pre-specified situations [refer to protocol Section 10.1.1]);
- A 25-week treatment period (Primary Analysis Period [PAP]);
- An up to 120-week Extension Treatment Period (ETP);
- An up to 4-week post-treatment observation period.

Figure 1 – Graphical Study Design

1.5 MODIFICATIONS TO THE STATISTICAL SECTION OF THE PROTOCOL

The current SAP is based on Protocol Amendment 03 Version 1 (dated 27 July 2018). This section summarizes major changes to the protocol statistical section with emphasis on changes after study start (after the first patient was enrolled on 26 October, 2017). The listing below gives the rationale and key details of major changes (e.g., substantial changes according to European Clinical Trial Applications guidance) to the protocol statistical section.

- Change to the sample size: Cap of 5 patients per cohort in Stage 1, Cohort 1 and Cohort 2, has been removed to alleviate constraints in conduct of the study and maximize the collection of data in pediatric patients. At least 10 patients will be included in Cohort 3.
- Change to endpoints: FLACC assessment has been removed from the protocol to reduce patient and investigational staff burden due to the limited expected value of the assessment.
- The baseline value is defined as the last non-missing value prior to first investigational medicinal product (IMP) intake, unless otherwise specified. This is true for PAP. However, in the ETP analyses, the ETP baseline value is defined as:
 - The last non-missing value prior to first IMP intake in PAP for patients receiving alglucosidase alfa from the beginning of this study;
 - The last non-missing value prior to first IMP intake in ETP for patients switching to alglucosidase alfa from alglucosidase alfa.
- The composite score constructed considering 3 domains: Gross Motor Function Measure-88 (GMFM-88) and Gross Motor Function Classification System - Expanded and Revised (GMFCS-E&R), Ptosis, and Respiratory Function serves as an exploratory endpoint.

Globally, reference to the investigational medicinal product (product code GZ402666) has been changed from neoGAA to its recommended International Nonproprietary Name, alglucosidase alfa.

1.6 STATISTICAL MODIFICATIONS MADE IN THE STATISTICAL ANALYSIS PLAN

The listing below gives the rationale and key details of major changes to Statistical Analysis Plan Version 1.0.

- In retrospective Chart Review, update “new onset of ptosis” to “presence of ptosis”.
- Update part of the definition of transient ADA response from “treatment induced ADA detected at two or more sampling time points during the treatment, where the first and last ADA-positive samples are separated by a period less than 16 weeks, and the patient’s last sample time point is ADA-negative” to “the last sample time point is positive and separated by <16 weeks from the first positive result”.
- Treatment-boosted ADAs are excluded from the analysis of ADA kinetics. If many patients have preexisting ADAs, kinetics of boosting will be described separately.
- The assessment of NAb response is simplified.

- Expand the composite score from cohort 3 to all population in [Table 1](#)
- Update the wording on re-randomization test for efficacy endpoints besides to composite score
- Update PCSA following ISS

2 STATISTICAL AND ANALYTICAL PROCEDURES

The interim analysis will be performed when all Cohort 3 patients have completed the 6-month (25 weeks) primary analysis period and will include a formal database lock and analyses of safety (including adverse events, physical examinations and growth, clinical laboratory evaluations, electrocardiogram [ECG], vital signs and immunogenicity), PK, efficacy (including GMFM-88, GMFCS-E&R, Pompe-Pediatric Evaluation of Disability Inventory [PEDI] mobility, Quick Motor Function Test [QMFT], echocardiography [ECHO], Eyelid position measurements including Interpalpebral fissure distance [IPFD], Margin reflex distance-1 [MRD-1], Margin pupil distance [MPD], total creatine kinase [CK], CK with MB fraction, and Composite Score Constructed Considering 3 Domains: GMFM-88 and GMFCS-E&R, Ptosis, and Respiratory Function), PD (urinary Hex4 level), and exploratory effect of avalglucosidase alfa treatment on functional endurance, six-minute walk test (6MWT), respiratory function (including Pulmonary Function Testing [PFT] and ventilator use diary), PedsQL Generic Core Scales, HRQOL, pain (including PedsQL Pediatric Pain Questionnaire and Visual Analogue Scale [VAS]), developmental disability (including Bayley Scale of Infant and Toddler Development, Third Edition [Bayley-III] and Leiter International Performance Scale, Third Edition [Leiter-3]), and hearing testing in patients with IOPD. A Clinical study report (CSR) will be prepared after the PAP analysis.

After the completion of primary analysis when all Cohort 3 patients have completed the 6-month (25 weeks) primary analysis period, interim analyses may be performed in ETP to provide additional information for regulatory purpose.

The final ETP analyses will be performed after all patients completed ETP. A final DBL will occur and a final CSR will be prepared after the ETP analyses.

2.1 ANALYSIS ENDPOINTS

2.1.1 Demographic and baseline characteristics

The PAP baseline value is defined as the last non-missing value prior to first investigational medicinal product (IMP) intake, unless otherwise specified.

The ETP baseline value is defined as:

- The last non-missing value prior to first IMP intake in PAP for patients receiving avalglucosidase alfa from the beginning of this study;
- The last non-missing value prior to first IMP intake in ETP for patients switching to avalglucosidase alfa from alglucosidase alfa.

Demographic characteristics

Demographic variables are age at study entry (year), gender (Male, Female), race (American Indian or Alaska Native, Asian, Black or Africa American, Native Hawaiian or other Pacific Islander, White, Not Reported), ethnicity (Hispanic, non-Hispanic, Unknown, Not Reported).

Medical or surgical history

Medical or surgical history includes prior or existing condition in different body systems as well as prior or existing medical conditions/surgical procedures of specific interest.

Disease characteristics at baseline

Pompe disease history includes acid α -glucosidase (GAA) genotyping, CRIM (cross-reactive immunologic material) status, GAA enzyme activity, [REDACTED], [REDACTED], aspects of disability (Pompe medical history, ventilator and assistive mobility device use), age at first symptoms of Pompe disease, age at diagnosis of Pompe disease, age at first treatment with alglucosidase alfa, time from Pompe disease diagnosis to first infusion of study drug, time from first symptoms of Pompe disease to first infusion of study drug.

Pompe medical history includes:

- Cardiovascular history (evidence of cardiac involvement, current NYHA (the New York Heart Association) heart failure classification, congestive heart failure),
- Ears, nose, throat medical history (enlarged tongue, hearing loss),
- Gastrointestinal (hepatomegaly, gastroesophageal reflux),
- Respiratory history (pneumonia, tracheostomy, sleep disturbances, sleep apnea),
- Musculoskeletal history (muscle weakness in upper extremities, muscle weakness in lower extremities, scoliosis, joint contractures, and current ambulatory status, assisted walking device and wheelchair use).

Family history of Pompe disease history includes confirmed Pompe disease in other family members.

Retrospective Chart Review

Retrospective review of available assessments prior to study entry documents clinical decline or suboptimal clinical response. It may include the following assessments:

- Respiratory function evaluation:
 - FVC (% predicted),
 - use of ventilator support.
- Motor function evaluation:
 - gross motor milestone,
 - GMFM-88 composite score,
 - Pompe-PEDI mobility,
 - QMFT,
 - GMFCS-E&R,

- other test or assessment, if any.
- Cardiac Function Evaluation:
 - Left ventricular mass (LVM) standard score (Z-score);
 - Left ventricular mass index (LVMI; g/m²);
- Other Evaluation:
 - Presence of ptosis.

The above assessments have documented (at least 2 recent and consecutive assessments prior to study entry, not less than 2 weeks apart) evidence of clinical decline or suboptimal clinical response in at least 1 of the following parameters related to Pompe disease and NOT related to intercurrent illness as assessed by the Investigator, in addition to at least 1 previous assessment prior to onset of decline:

- For patients entering Stage 1 - clinical decline in at least 1 of the following parameters: respiratory function, motor skills, and/or cardiac parameters.
- For patients entering Stage 2 - suboptimal clinical response in at least 1 of the following parameters: respiratory function, motor skills, and/or presence of ptosis.

Growth parameters at baseline

Weight (kg), height/total body length (cm), body mass index (BMI, kg/m²), head circumference (cm) and Tanner stage of sexual maturation.

Vital signs

Vital signs include systolic blood pressure, diastolic blood pressure, heart rate, respiratory rate, temperature, and oxygen saturation. The baseline values for vital signs are the last non-missing assessment prior to the first study treatment by comparing the infusion time and measurement time.

Immunogenicity status

The immunogenicity evaluation at baseline includes antibody status (positive or negative) and magnitude (titer) of the anti-drug antibodies (ADA).

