- e Retrospective chart review at screening/baseline to collect available data on clinical decline or sub-optimal clinical response as outlined in [I 06](#) and [I 07](#).
- f Enrollment of patients in Cohorts 1 and 2 and randomization of patients in Cohort 3: IRT contact will be performed anytime during screening period for screening, prior to IMP administration for all other concerned visits and on or before Day 1 for enrollment/randomization.
- g Biweekly administration or, for alglucosidase alfa in Cohort 3 only, weekly administration (current stable dose). For all patients, all visits following V2 (Day 1) are calculated from the day of first infusion of investigational medicinal product (IMP) in 14-day increments with a window of \pm 7 days (in Cohort 3 participants, 7 day increments with a window of \pm 3 days for weekly (qw) alglucosidase alfa treatment) for infusions and safety assessments and \pm 14 days for all other assessments.
- h Female patients of childbearing potential only will have serum test for pregnancy at Screening, a urine β -hCG test up to 24 hours before D1 infusion and every 4 weeks thereafter.
- i Physical examination CRF will ask physician to record current muscle pain and cramps specifically at each PE assessment. Tanner stage will be assessed as part of the PE assessment at screening/baseline.
- j To be measured at screening/baseline, every 3 months up to Week 73 and then every 6 months until Week 145/EOS in all patients.
- k At every infusion. Vital signs include heart rate, systolic and diastolic blood pressure, respiratory rate, temperature, and oxygen saturation and are to be assessed prior to infusion, with each infusion rate change, at the end of the infusion and at the end of the post-infusion observation period. Collection windows are \pm 15 minutes.
- l 12-lead ECG after at least 15 minutes in supine position (if supine is feasible for the patient). Review should be done at the site in a timely manner to determine if there are any safety concerns and for clinical management of the patient. In addition, reading will be done by central reader for analyses purposes only.
- m 12-lead ECG after at least 15 minutes in supine position (in triplicate predose at Day 1 only) and prior to receiving IMP: 3 ECGs within 5 minutes will be performed with at least 1 minute between 2 replicates.
- n Biochemistry panel will include BNP and CK.

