11.4.2 Analyses of safety data

In general, for the PAP, the summary of safety results will be presented by study cohort/treatment arm within each stage, as well as by dose levels among the avalglucosidase alfa-treated patients. For the overall avalglucosidase alfa treatment period, the summary of safety results will be presented by dose levels among avalglucosidase alfa patients. All safety results that have been collected at the time of the analysis will be included for the overall treatment period summaries. For Cohort 3 alglucosidase alfa patients, the summary of safety results for the extension period will be presented separately. Safety endpoints are presented in [Section 9.1.1](#).

All safety analyses will be performed on the safety population using the following common rules:

The baseline value is defined as the last non-missing value prior to first IMP intake. Further details will be provided in the SAP.

The following definitions will be applied to laboratory parameters, vital signs and ECG.

- The potentially clinically significant abnormality (PCSA) values are defined as abnormal values considered medically important by the Sponsor according to pre-defined criteria/thresholds based on literature review and defined by the Sponsor for clinical laboratory tests, vital signs, and ECG.
- PCSA criteria will determine which patients had at least 1 PCSA during the on-treatment period, taking into account all evaluations performed during the on-treatment period, including unscheduled or repeated evaluations. The number of all such patients will be the numerator for the on-treatment PCSA percentage.

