Standard 12-lead ECGs are recorded after at least 15 minutes in the supine position using an electrocardiographic device. The following will be assessed: heart rate, rhythm, interval from start of the Q wave to the end of the S wave (QRS), interval between the peaks of successive QRS complexes (RR), interval from the beginning of the P wave until the beginning of the QRS complex (PR), interval between the start of the Q wave and the end of the T wave (QT), QT interval corrected for heart rate (QTc) automatic correction evaluation (both Fredericia and Bazett corrections by the ECG device), QRS axis, left ventricular hypertrophy criteria, right ventricular hypertrophy criteria, repolarization charges, and overall cardiac impression for each patient. For Day 1 only, and prior to receiving IMP, 3 ECGs within 5 minutes will be performed with at least 1 minute between 2 replicates.

2.1.3.6 *Physical examination*

Physical examination parameters include assessments of the patient's general appearance; skin; head, eyes, ears, nose, and throat; examinations of lymph nodes, abdomen, extremities/joints, neurological and mental status; heart and respiratory auscultation; peripheral arterial pulse; and pupil, knee, Achilles, and plantar grasp reflexes. Physical examination e-CRF also asks physician to record current muscle pain and cramps specifically at each PE assessment. Tanner stage of sexual maturation will be assessed as part of the PE assessment at baseline and yearly thereafter.

2.1.3.7 *Body weight, height/total body length, and head circumference*

Body weight will be measured in kilograms and collected monthly throughout the duration of the study. More frequent weight may be obtained at the discretion of the Investigator.

Standing height or total body length will be measured at baseline and every 3 months up to Week 73 and then every 6 months and at the end of study. If possible, height will be measured in the morning of the study visit day, prior to the PFT, and by using the same stadiometer for all measurements. Standing height is preferred, but if not possible due to patient's age or physical condition, total body length is to be measured in the same position throughout the study.

BMI will be calculated as the body weight divided by the square of the body height.

Head circumference will be measured at the same time points.

2.1.3.8 *Immunogenicity*

Immunogenicity assessments will include the following:

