2.4.4 Analyses of safety data

In general, for PAP, the summary of safety results will be presented by study cohort and treatment arm. For the overall avalglucosidase alfa treatment period, the summary of safety results will be presented by initial planned dose levels among avalglucosidase alfa patients. For Cohort 3 alglucosidase alfa patients, the summary of safety results for ETP will be presented in separate tables.

In the PAP analysis, the safety analyses will be carried out with patients by the actual treatment received, irrespective of the treatment the patient has been randomized to. The actual treatment received is defined as:

- avalglucosidase alfa if the patient receives at least one infusion with this drug in PAP;
- alglucosidase alfa if the patient only receives alglucosidase alfa in PAP.

In the ETP analysis and/or overall evaluation of avalglucosidase alfa safety, the safety analyses will be carried out by the following 3 groups:

- AVAL/AVAL in ETP includes data in ETP among patients who received avalglucosidase alfa in PAP and ETP;
- ALGLU/AVAL in ETP includes data in ETP among patients who received alglucosidase alfa in PAP and received avalglucosidase alfa in ETP;
- AVAL/AVAL and ALGLU/AVAL in overall avalglucosidase alfa treatment period includes data in PAP and/or ETP among patients who received avalglucosidase alfa in that period.

General rules

All safety analyses will be performed on the safety population as defined in [Section 2.3.1](#), unless otherwise specified, using the following common rules:

- The safety baseline value is defined the same as the baseline definition in [Section 2.1.1](#).
- The potentially clinically significant abnormality (PCSA) values are defined as abnormal values considered medically important by the Sponsor according to predefined criteria/thresholds based on literature review and defined by the Sponsor for clinical laboratory tests, vital signs, and ECG (PCSA version dated January 2014 [[Appendix B](#)]).
 - PCSA criteria will determine which patients had at least 1 PCSA during the treatment epoch (for PAP and ETP respectively), taking into account all evaluations performed during this period, including nonscheduled or repeated evaluations.
 - The number of all such patients will be the numerator for the on-treatment PCSA percentage; the denominator will be the number of patients assessed for that given parameter in the treatment epoch by treatment group on the safety population.

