2.5 DATA HANDLING CONVENTIONS

2.5.1 General conventions

In general, the baseline value is defined as latest non-missing value prior to the start of first infusion in PAP or ETP ([Section 2.1.1](#)). In the case an assessment performed on the same date as the first infusion date, but it is impossible to determine the evaluation time relative to first infusion start time, the evaluation time will be assumed to follow the protocol-defined schedule.

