2.5.4 Windows for time points

The visit windows for efficacy endpoints are defined in the following table. For analysis purpose, a larger window (as shown in the last column of [Table 5](#)) will be used. This will be applicable for those analyses requiring visit information.

The analysis visit will be defined by comparing the actual visit date with the nominal (or target) date and the corresponding analysis window from [Table 5](#). If more than one non-missing value is assigned to the same visit, then the one closest to the target date will be used in the by-visit analysis. Multiple values on the same date will be averaged first. If two assessments are on different dates but equal distance from the target date, the later date will be used.

For the safety analyses (laboratory, ECG and vital signs), the nominal visit will be used for the by-visit type of analyses.

Table 5 - Study visit nominal visit days and windows for efficacy endpoints

Scheduled Visit	Visit window defined in protocol in study days	Visit window for analysis purpose in study days
Screening/Baseline	Day -14 to -1	-28 to -1 (or 1 if before 1st infusion)
Week 13	Day 85 ±14	Day 0 (or Day 2 if Screening/baseline on Day 1) to 85 + 41
Week 25	Day 169 ±14	Day 169- 42 to 169 + 41 and prior to any ETP treatment
Week 37	Day 253 ±14	Day 253- 42 to 253 + 41 and after the 1st ETP treatment
Week 49	Day 337 ±14	Day 337- 42 to 337 + 41
Week 61	Day 421 ±14	Day 421 - 42 to 421 + 41
Week 73	Day 505 ±14	Day 505 - 42 to 505 + 83
Week 97	Day 673 ±14	Day 673- 84 to 673 + 83
Week 121	Day 841 ±14	Day 841- 84 to 841 + 83
Week 145	Day 1009 ±14	Day 1009- 84 to 1009 + 83 ±84

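### The baseline rule, read literally, uses one of the three pre-dose Day 1 ECGs; averaging them is a free but small gain in precision

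*SAP*

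**What the plan says.** **Collection.** SAP 2.1.3.5 states: "For Day 1 only, and prior to receiving IMP, 3 ECGs within 5 minutes will be performed with at least 1 minute between 2 replicates". Protocol 9.1.1.4 has the same requirement, and the ECG footnote in Protocol 1.2.1 limits it: "in triplicate predose at Day 1 only". Later scheduled ECGs are single recordings. Protocol 10.1.1 lists no screening ECG, so the triplicate is the only scheduled ECG before treatment.

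**Baseline.** Protocol 11.4.2 gives the rule and defers the detail: "The baseline value is defined as the last non-missing value prior to first IMP intake. Further details will be provided in the SAP". SAP 2.1.1 repeats it: "The PAP baseline value is defined as the last non-missing value prior to first investigational medicinal product (IMP) intake, unless otherwise specified". SAP 2.4.4 extends it to safety data: "The safety baseline value is defined the same as the baseline definition in" Section 2.1.1. SAP 2.5.1 restates it: "the baseline value is defined as latest non-missing value prior to the start of first infusion in PAP or ETP". None of these mentions replicates, and neither ECG section (SAP 2.1.3.5 and 2.4.4.5) takes up the exception that 2.1.1 leaves open.

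**Averaging.** SAP 2.5.4 has one sentence that averages values from the same date. It belongs to the assignment of analysis visits through Table 5, which is for efficacy endpoints. A separate paragraph then says: "For the safety analyses (laboratory, ECG and vital signs), the nominal visit will be used for the by-visit type of analyses".

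**Use.** SAP 2.4.4.5 summarises ECG changes from baseline and counts potentially clinically significant abnormalities (PCSAs) on the worst value. In the paediatric column of Appendix B, QTc (rises of 30 to 60 ms and above 60 ms) and heart rate (change of at least 20 bpm) depend on baseline. PR and QRS do not.

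**The concern.** When all three recordings exist, the last non-missing one is the third. Its full recording error then enters every later change for that patient, although two further recordings from the same session are available to reduce it.

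For patients on avalglucosidase alfa from the start, SAP 2.1.1 keeps the Day 1 baseline through the extension treatment period (ETP). For them the effect lasts beyond the primary analysis period (PAP). Safety is the primary objective and ECG is one of its listed components. Groups may be as small as 5 patients, so one chance flag can be 20% of a group.

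**Working it through.** The plan gives no QTc SD and no expected flag rate, so there is no stated figure to reproduce.

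**Inputs from the documents**
- Three replicates on Day 1, single ECGs afterwards.
- Three scheduled PAP ECGs after baseline: Weeks 5, 13 and 25 (Protocol 10.1.2.5 and 10.1.2.6).
- Five more in the ETP for patients on avalglucosidase alfa from the start: Weeks 49, 73, 97, 121 and 145 (Protocol 10.1.3.7).
- About 20 patients.

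**Assumptions**
- Single-ECG SD s of 10, 15 or 20 ms, with normal errors and no true change.
- A share f of s² arises between replicates in one session. The rest is common to all three.

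**Precision**
- Variance of one baseline ECG: s². Variance of the mean of three: (1 − f)s² + f·s²/3 = (1 − 2f/3)s².
- Variance of a change: 2s² under the written rule, (2 − 2f/3)s² with the mean.
- Ratio of SDs: √(1 − f/3).

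| f | SD ratio | Reduction |
|---|---|---|
| 0.25 | √0.917 = 0.957 | 4% |
| 0.5 | √0.833 = 0.913 | 9% |
| 1 (ceiling) | √0.667 = 0.816 | 18% |

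**Chance flags, increase criterion alone.** With baseline error B, the chance that at least one of k ECGs lies more than 30 ms above baseline is 1 − E[Φ((30 + B)/s)^k]. The variance of B is s² or (1 − 2f/3)s². By numerical integration for k = 3:

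| s (ms) | Single | Mean, f = 0.25 | Mean, f = 0.5 | Mean, f = 1 |
|---|---|---|---|---|
| 10 | 4.4% | 3.6% | 2.8% | 1.4% |
| 15 | 17.7% | 16.4% | 14.9% | 11.2% |
| 20 | 29.8% | 28.7% | 27.5% | 24.1% |

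At f = 0.5 this is 20 × 0.016 = 0.3, 20 × 0.029 = 0.6 and 20 × 0.023 = 0.5 fewer chance flags in 20 patients. The largest difference in the table is 20 × 0.065 = 1.3 (s = 15, f = 1).

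For rises above 60 ms at f = 0.5, the rates are about 0 either way (s = 10), 0.7% against 0.3% (s = 15) and 4.4% against 2.8% (s = 20). Over all eight ECGs (k = 8, above 30 ms, f = 0.5) they are 9.0% against 6.3%, 30.9% against 28.2%, and 47.1% against 46.5%.

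**Chance flags, joint criterion.** Appendix B prints AND between the paediatric absolute QTc value and the increase. If both are needed, an ECG must exceed 430 ms and also lie more than 30 ms above baseline. The chance becomes 1 − E[Φ(max(30 + B, 430 − m)/s)³], where m is an assumed mean QTc. At f = 0.5:
- m = 420 ms, s = 15: 16.0% single, 14.1% averaged.
- m = 400 ms, s = 15: 4.25% single, 4.42% averaged.
- m = 400 ms, s = 20: 12.4% single, 12.9% averaged.

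At m = 400 ms a baseline that is low by chance cannot bring the hurdle below 430 ms, while one that is high by chance raises it. Averaging removes some of that raising, so flags go up slightly.

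**The case against.** The strongest reply is that this is an unstated derivation with little depending on it. Several stronger readings are tempting, and the documents do not support them.

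- **That the SAP chooses the third ECG.** No sentence says so. It follows from applying the general rule to three recordings, and a programmer might borrow the same-date averaging sentence from SAP 2.5.4.
- **That SAP 2.5.4 bars ECG averaging.** It does not. The safety paragraph only fixes which visit label applies. The averaging sentence nevertheless sits under efficacy visit windows, so it cannot be relied on for ECG.
- **That the documents give the triplicate the purpose of stabilising baseline.** They state no purpose.
- **That averaging always reduces chance flags.** This holds for the increase criterion alone. Under the joint paediatric reading it can fail, as the 400 ms cases show. Patients are under 18 at entry, so that column is the relevant one.
- **That the gain is 18% in SD.** That needs fully independent replicate error. Recordings minutes apart are likely to share part of it.

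It also stands that the safety analysis is descriptive without inferential testing (SAP 2.4.4), that ECG measurements are listed individually, that absolute cut-offs applied alone do not use baseline, and that an abnormal ECG is rechecked before permanent discontinuation (Protocol 10.3.3). These points lower the priority. They do not remove the loss of precision, which exists for any non-zero replicate variance.

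**Conclusion.** The point holds as a minor one. The written rule uses one of three available pre-dose recordings, so every ECG change from the Day 1 baseline is noisier than it need be, in the PAP and, for patients on avalglucosidase alfa from the start, in the ETP. That direction is certain if replicates vary at all.

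The size rests on assumed values of s and f. The reduction in SD is at most 18% and more plausibly 4 to 9%. On the increase criterion alone, that more plausible range means less than one chance flag above 30 ms in 20 patients over the PAP. No firm claim about flags is possible until the SAP says whether the paediatric QTc criteria are joint or separate.

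**What to change.** Add to SAP 2.1.1 or 2.4.4.5: for ECG intervals and heart rate, the Day 1 baseline is the mean of the available pre-dose replicates, or the last earlier value if there are none. For patients who switch from alglucosidase alfa, keep the last ECG before the first ETP dose as the ETP baseline, because no triplicate is scheduled there. In Appendix B, state whether the paediatric QTc absolute value and increase must both be met or are counted separately.

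The cost is two or three SAP sentences and a small programming change. The recordings are already required and centrally read (Protocol 9.1.1.4), so patients bear no added burden.
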